17. DATA ANALYSIS PLAN

To assess feasibility, the primary outcome of this study, we chose a sample size of 20. To infer feasibility, at least 50% of the sessions should be performed successfully per subject for at least 70% of the subjects. This criterion is based on a study that reported dropout rates between 22% and 25% of home-based tDCS for patients with bipolar depression (40) and that therapeutic effects with tDCS could be achieved within one week of treatment (24). For each time point established, we will compare groups with a t-test or chi-square test, for continuous and categorical data, respectively (a p value<0.05 will be considered significant).

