4. STUDY DESIGN

This is a single-center, randomized, sham-controlled, double-blind clinical study to investigate the feasibility of delivering RS-tDCS sessions for high-risk patients for suicide in the days following discharge from the CPEP or inpatient unit which they were admitted with SI or attempt. We plan to assess up to 80 adult patients for eligibility over 12 months of which 20 will be enrolled and randomized. Clinical assessments will be performed at baseline, post-treatment day 14 (14 days after the first RS-tDCS session), and follow-up day 30 and 60 (30 and 60 days after the first RS-tDCS session, respectively).

All study outcome measures are described in Table 1.

Time points		in-person	remote	
	Measures		S1 to S10	C14, C30, and C60
Eligibility screening		Х		
Informed consent		Х		
Enrollment		Х		
		Baseline		
Demographic data		Х		
General medical history		X		
Orientation tDCS session		X		
Loan agreement		Х		
	Feasibility		X*	
	C-SSRS	X		Х
	RRS	X		Х
	CAST	Х		Х
	MADRS	Х		Х
	C-SSRS SV		X	
	Side effects questionnaire		X	
	Treatment emergent event review		Х	Х
	Acceptability questionnaire		X**	
	Blinding assessment		X**	

Table 1. Study's time points and measures.

C14, C30, and C60: clinical assessments at post-treatment day 14, follow-up day 30 and follow-up day 60; CAST: The Concise Associated Symptoms Tracking; C-SSRS: The Columbia-Suicide Severity Rating Scale; C-SSRS SV: The Columbia-Suicide Severity Rating Scale – screening version; MADRS: Montgomery-Asberg Depression Rating Scale; RRS: Ruminative Responses Scale; S1 to S10: remotely supervised transcranial direct current stimulation (RS-tDCS) sessions one to ten.

*Number of completed RS-tDCS sessions per participant within three weeks of the study.

**applied only once, after the final RS-tDCS session (the tenth session).

Primary outcome measures:

Page 5 of 22 Version Date: 10/09/2023 1. Feasibility of the intervention – number of completed remotely supervised transcranial direct current stimulation (RS-tDCS) sessions, for both active and sham groups:

We expect at least 70% of the subjects to complete at least 5 of recommended 10 RS-tDCS sessions within three weeks of receiving the home-based tDCS device.

This criterion is based on a study that reported dropout rates between 22% and 25% of homebased tDCS for patients with bipolar depression (40) and that therapeutic effects with tDCS could be achieved within one week of treatment (24).

Secondary outcome measures:

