1. Intensity of suicidal ideation as assessed by the Columbia Suicide Severity Rating Scale (C-SSRS) (41) (time frame: day 14 [+ 7 days], day 30 [+ 7 days], and day 60 [+ 10 days] from the first RS-tDCS session):

The C-SSRS is a suicidal ideation and behavior rating scale with yes/no responses. For each of the 5 items of the C-SSRS related to suicidal ideation intensity, an individual's degree of suicidal ideation is rated on a 0-5 scale. The total score is the sum of the 5 intensity item scores (total score ranges from 0 to 25), with higher scores indicating more severe suicidal ideation.

2. Acceptability based on subject's readiness, self-confidence, and satisfaction in dealing with the device and RS-tDCS sessions. Acceptability based on subject's readiness, self-confidence, and satisfaction will be considered if at least 60% of all subject's rate "strongly agree" or "agree" on the questionnaire item 11: "Overall, I felt that transcranial electrical stimulation treatment benefited me" (the questionnaire is a 5-item Likert scale with the following response options "Strongly agree", "Agree", "Neither agree nor disagree", "Disagree", "Strongly disagree") (42). These questions were adapted from other studies with home-based tDCS (37, 43) and will be presenting as following: 1) "It was easy to prepare the device and accessories"; 2) "I felt confident setting up the stimulation sessions"; 3) "I felt confident using the device"; 4) "I needed to learn a lot of things before I could get going with this device"; 5) "The device was unnecessarily complex"; 6) "I could find a convenient time to do the stimulation sessions"; 7) "I would imagine that most people would learn to use this device quickly"; 8) "The stimulation sessions interfered with my everyday life"; 9) "It would have helped to have more in-person, one-on-one instruction"; 10) "I felt that the remote supervision sessions were helpful"; 11) "Overall, I felt that transcranial electrical stimulation treatment benefited me". Questions 4, 5, 8, and 9 will be reverse coded. This information will be collected after the final RS-tDCS session (that is, the tenth RS-tDCS session).15

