3. Proportion of patients who answered "no" for both questions 1 ("Have you wished you were dead or wished you could go to sleep and not wake up?") and 2 ("Have you actually had any thoughts of killing yourself?") of the C-SSRS (time frame: day 14 [+ 7 days], day 30 [+ 7 days], and day 60 [+ 10 days] from the first RS-tDCS session). This will help to determine the proportion of subjects who presented suicidal ideation relapse since the negative answer for both questions will be an inclusion criterion for this study.

4. Intensity of rumination as assessed by the Ruminative Responses Scale (RRS) (44) (time frame: day 14 [+ 7 days], day 30 [+ 7 days], and day 60 [+ 10 days] from the first RS-tDCS session):

The RRS encompasses 22 items. Each item is rated on a 4-point Likert scale: 1, almost never; 2, sometimes; 3, often; 4, almost always. The score on this scale is obtained by simply summing the scores on the 22 items.

5. Symptoms associated with suicidal ideation as assessed by the Concise Associated Symptoms

Tracking (CAST) scale (time frame: day 14 [+ 7 days], day 30 [+ 7 days], and day 60 [+ 10 days] from the first RS-tDCS session):

The 16 items of the CAST Scale assess symptoms across five domains: anxiety (three items, subscore range 3-15), irritability (five items, subscore range 5-25), mania (four items, subscore range 4-20), insomnia (two items, subscore range 2-10), and panic (two items, subscore range 2-10). The total CAST score ranges from 16 to 80. Each item is rated on a 5-point Likert scale: 1, strongly disagree; 2, disagree; 3, neither agree nor disagree; 4, agree; or 5, strongly agree, with higher scores indicating more severe symptoms.

6. Depressive symptoms as assessed by the Montgomery-Asberg Depression Rating Scale (MADRS) (time frame: day 14 [+ 7 days], day 30 [+ 7 days], and day 60 [+ 10 days] from the first RS-tDCS session):

MADRS is a 10-item questionnaire that includes questions on the following symptoms: 1. Apparent sadness 2. Reported sadness 3. Inner tension 4. Reduced sleep 5. Reduced appetite 6. Concentration difficulties 7. Lassitude 8. Inability to feel 9. Pessimistic thoughts 10. Suicidal thoughts. Each item yields a score of 0 to 6. The overall score ranges from 0 to 60. A higher MADRS score indicates more severe depression. The usual cutoff points are:

0 to 6 - normal/symptom absent; 7 to 19 - mild depression; 20 to 34 - moderate depression; >34 - severe depression.

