8. STUDY PROCEDURES

The pre-screening will be carried out through the electronic hospital medical record to identify potential subjects. Once the potential subject is identified, research staff will visit the unit where the patient is receiving treatment (inpatient unit or CPEP) and talk with unit staff in person, providing information about the study. Then, the research staff will ask unit staff to determine the most appropriate time for the research staff to meet with the patient based on knowledge of patient status and needs.

[figure not shown]
After screening and signing consent, the research study staff will collect demographic and general medical history data, apply the clinical questionnaires, and conduct the orientation tDCS session as part of the in-person baseline assessment (Table 1 and Figure 3). This demographic, general medical history, and clinical data will be collected and stored in the REDCap through a tablet or another portable electronic device. Per subject need/request, research study staff reads aloud instructions and questions while subjects hold the tablet to record their answers. If the REDCap site is down or malfunctioning, screening, consent, and questionnaires are completed on paper and later entered into REDCap.

The orientation session includes presenting the Soterix Medical mini-CT device to the subject to show how to turn it on/off, how to insert the device unlock codes for one-time use, how to correctly adjust the SNAPstrap headgear, and answer any questions they may have. As part of the orientation session, research staff will also conduct a 90-s tolerability test, with 2.0 mA as the starting point (electrical current intensity of the study protocol). During this test, the current intensity is ramped up to 2.0 mA and the subject will receive the stimulation for 90 seconds. The tolerability will be determined by subject rating below 7 on the 0-10 Visual Analogue Scale (VAS) of pain. If the subject finds the target tDCS dose intolerable (i.e., VAS 7 or higher), subjects will have the option of another test, with the amperage dose decreased by 0.5 mA (i.e., to 1.5 mA). If this lower amperage is also intolerable, the subject will be excluded from the study (39, 46). Thus, the orientation session aims to 1) familiarize the subject with the

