device, how to turn it on/off, and insert the unlock codes for one-time use; 2) to assess if the subject tolerates the protocol electric current through the tolerability test; 3) answer any questions the subjects may have. As the Soterix Medical mini-CT device will be with the subjects during the RS-tDCS sessions, subjects will be asked to sign an IRB-approved device loan agreement at the baseline.

Clinical questionnaires will be re-administered at day 14 [+ 7 days], day 30 [+ 7 days], and day 60 [+ 10 days] from the first RS-tDCS session session15 (Figure 3). While we aim to reach subjects on the phone for follow-up, research staff may email or text subjects to schedule the RS-tDCS sessions and clinical assessments. Subject identifying information and protected health information (PHI) is not exchanged in the text messages themselves. Detailed information about text messaging is included under the "Privacy and Confidentiality of Subjects and Research Data" section. Security risks associated with text messaging are described in detail during consent.

After baseline assessment, research staff not involved in the RS-tDCS supervisions and clinical assessments will randomize the subject to active or sham control group and set up the device condition (active or sham), program the intensity for the active condition (either 2.0 mA or 1.5 mA, according to the tolerability test) and duration (30 minutes) of each session, and get the device unlock codes for one-time use to be provided by the research staff to the subject immediately before each session. The discharge day will be tracked daily by the research staff through the electronic hospital medical record. Once the subject is discharged, research staff will deliver the RS-tDCS device by mail to the subject's address in a pre-paid FedEx package to send it back and contact the subject once the device has arrived at their home (by using the mail tracking number) to schedule the first RS-tDCS session.

*device set up for the condition (active or sham), and locked (unlock codes for one-time use will be provided before each session); **day 1 being the first RS-tDCS session and no sessions on weekends. CPEP: Comprehensive Psychiatric Emergency Program; DLPFC: dorsolateral prefrontal cortex; RS-tDCS: remotely supervised transcranial direct current stimulation.

RS-tDCS sessions:

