Clinical assessments with be performed at day 14 [+ 7 days], day 30 [+ 7 days], and day 60 [+ 10 days] from the first RS-tDCS session with the questionnaires described in Table 1. Thus, the duration of and individual's participation in the study will be up to 70 days.

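### RRS, CAST and MADRS are compared by unadjusted t-tests with no confidence interval, although pre-randomization baselines exist; ANCOVA on own baseline would be a cheap gain in precision if the baseline-outcome correlation exceeds about 0.25 to 0.30

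*Combined protocol and SAP*

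**What the plan says.** Section 17 (Data Analysis Plan) sets the sample at 20 for the feasibility outcome and then states: "For each time point established, we will compare groups with a t-test or chi-square test, for continuous and categorical data, respectively", with significance at p < 0.05. It names no covariate and does not say whether scores or changes from baseline are tested. No confidence interval is planned there or elsewhere in the text available for review.

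Table 1 in section 4 marks C-SSRS, RRS, CAST and MADRS at the in-person baseline and at the three later clinical assessments. Section 8 has staff "apply the clinical questionnaires, and conduct the orientation tDCS session as part of the in-person baseline assessment". Allocation comes next: "After baseline assessment, research staff not involved in the RS-tDCS supervisions and clinical assessments will randomize the subject". The baseline scores therefore cannot be affected by treatment.

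Hypothesis 2 (section 1) expects less intense ideation on the C-SSRS in the active arm at the end of treatment, and intends the result to supply an effect size for sizing a full randomized trial. Section 5 admits only subjects who answer no to C-SSRS questions 1 and 2.

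**The concern.** When a continuous outcome is also measured before randomization, part of its variation between subjects can be predicted from the baseline value. A t-test on the follow-up score leaves that part in the error term; ANCOVA removes it for one degree of freedom. With 20 subjects or fewer, intervals are wide, so precision available from data already collected is worth having. At this size, however, the degree of freedom is not negligible, and ANCOVA helps only if the correlation is large enough. The gain therefore has to be computed for this sample.

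C-SSRS intensity is a different case. Entry requires absence of ideation, so its baseline should have little spread and adjustment would do little. What is missing there is an interval. It is the one scale whose effect size is meant to feed a later sample size calculation, and a p-value does not show how uncertain that effect size is.

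**Working it through.** **Inputs.** From the documents: 20 subjects (section 17), 1:1 allocation (section 4.1), significance level 0.05 (section 17; two-sided assumed). Section 17 cites "a study that reported dropout rates between 22% and 25% of home-based tDCS for patients with bipolar depression"; 20 × 0.78 = 15.6 and 20 × 0.75 = 15. The cases with 16 (8/8) and 15 (8/7) analysed assume that this dropout carries over to the clinical assessments, which the documents do not say. The correlation r between baseline and follow-up is also an assumption, shown as a range. The plan gives no power, SD or correlation for any between-group comparison, so there is no figure of its own to reproduce.

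**Formulas.** Widths are in units of the outcome SD, under normality, where c4(v) is the expected sample SD on v degrees of freedom divided by the true SD.

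- t-test: mean 95% width = 2 · t(0.975, N−2) · c4(N−2) · √(1/n1 + 1/n2)
- ANCOVA: mean 95% width = 2 · t(0.975, N−3) · c4(N−3) · √(1−r²) · E[√(1/n1 + 1/n2 + D²/Sxx)], where D is the baseline mean difference and Sxx the within-arm baseline sum of squares

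**Numbers for 10/10.**

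- t-test: 2 × 2.1009 × 0.9862 × 0.4472 = 1.853
- ANCOVA at r = 0: 2 × 2.1098 × 0.9854 × 0.4605 = 1.915
- ANCOVA at r = 0.5: 1.915 × √0.75 = 1.658
- Break-even: √(1 − (1.853/1.915)²) ≈ 0.25

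**Mean 95% interval width (SD units).**

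| Analysed | t-test | ANCOVA r=0 | r=0.2 | r=0.3 | r=0.5 | r=0.7 | Break-even r |
|---|---|---|---|---|---|---|---|
| 10/10 | 1.853 | 1.915 | 1.876 | 1.827 | 1.658 | 1.368 | 0.252 |
| 8/8 | 2.107 | 2.202 | 2.158 | 2.101 | 1.907 | 1.573 | 0.291 |
| 8/7 | 2.194 | 2.303 | 2.256 | 2.197 | 1.994 | 1.644 | 0.304 |

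At r = 0.3, 0.5 and 0.7, ANCOVA is narrower by 1%, 10% and 26% with 10/10, by 0%, 9% and 25% with 8/8, and by 0% (marginally wider), 9% and 25% with 8/7. At r = 0 it is wider by 3%, 4.5% and 5% respectively. Simulation with bivariate normal data (100,000 trials per case) agrees with these widths and gives 95% coverage for both methods.

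**The gain is an average.** Share of simulated trials in which the ANCOVA interval is the narrower one:

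| Analysed | r=0 | r=0.2 | r=0.3 | r=0.5 | r=0.7 |
|---|---|---|---|---|---|
| 10/10 | 20% | 33% | 48% | 80% | 97% |
| 8/8 | 19% | 30% | 42% | 72% | 94% |
| 8/7 | 19% | 29% | 40% | 70% | 93% |

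**If change scores were meant.** With equal SDs at both visits, the t-test width is multiplied by √(2−2r). For 10/10 this gives 2.19, 1.85 and 1.44 at r = 0.3, 0.5 and 0.7, so ANCOVA is 17%, 10% and 5% narrower.

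**C-SSRS intensity.** By the noncentral t, an observed standardized difference of 0.5 has a 95% interval of −0.40 to 1.38 with 10/10 and −0.54 to 1.52 with 8/7. This rests on normality, which is doubtful here. A check with many zeros (assumed: only some subjects have ideation, with scores uniform from 5 to 20) gives coverage of the ordinary t interval of 0.93 (10/10) and 0.90 (8/7) when 10% of one arm and 30% of the other have ideation. With 10/10 and 20% to 50% in both arms, coverage is 0.95 to 0.96. If 10% have ideation in each arm, every score is zero and no interval exists in 0.9²⁰ = 12% of trials with 20 analysed, or 0.9¹⁵ = 21% with 15.

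**The case against.** The best defence is that nothing here is wrong. The t-test is valid, and its interval would already allow for chance baseline imbalance. The sample was chosen for feasibility, Aim 2 seeks only a preliminary signal, and RRS, CAST and MADRS play no part in sizing the next trial. All of that stands, and it is why this is a recommendation and not a correction.

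The gain also depends on an unknown r, and the design gives reasons for a low one. Baseline is taken in hospital, before discharge and mailing of the device, and the last assessment falls at "day 60 [+ 10 days] from the first RS-tDCS session with the questionnaires described in Table 1". At r = 0.3 the methods are level on average. This stands too. It makes the benefit conditional, but the possible loss (3% to 5% at r = 0) is small beside the possible gain.

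The natural reading of section 17 is that scores at each visit are tested, so the change-score comparison may describe an analysis nobody intended. That is fair; it matters only because the text leaves the point open.

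The simulations of ANCOVA assume normal data, whereas the scales are bounded, and skewness or unequal slopes with 7 to 10 per arm were not examined. For C-SSRS, calling an interval indicative does not repair its coverage when most scores are zero. Both are real limits. The second is a reason to present that interval with care, not to omit it.

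**Conclusion.** The point holds as an inexpensive improvement to three secondary analyses. Section 17 leaves pre-randomization baselines unused and plans no interval. ANCOVA would be more precise on average if r exceeds about 0.25 with 20 analysed, or about 0.30 with 15 or 16. The expected narrowing is about 9% to 10% at r = 0.5 and 25% to 26% at r = 0.7.

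It does not make this a precise comparison: at r = 0.5 with 10/10 the mean half-width falls only from 0.93 to 0.83 SD. Feasibility conclusions do not change. Confidence is medium, because r is not in the documents and may fall by day 60. The figures assume approximate normality, a two-sided 0.05 level and near-equal arms. The case for reporting a C-SSRS interval does not depend on r; it follows from the use that Hypothesis 2 intends for the estimate.

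**What to change.** - **RRS, CAST and MADRS.** At each of days 14, 30 and 60, fit ANCOVA with treatment arm and the same scale's baseline as the single covariate. Report the adjusted mean difference with its 95% confidence interval. Fix the covariate in the SAP before unblinding. The adjusted difference is the same whether the score or its change from baseline is the response, so this also settles what section 17 leaves unsaid.
- **C-SSRS intensity at day 14.** Report the unadjusted difference with a 95% confidence interval, and the mean and SD in each arm so that a standardized effect can be formed. Label the interval indicative, because subjects enter without ideation and many zeros are plausible. State what will be reported if all scores are zero.

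The cost is a few lines of SAP text, one model term and one degree of freedom per visit-specific model. The downside is the slight widening shown above if r is below break-even. No additional data are needed, and reporting the C-SSRS interval costs nothing.

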7. The level of side effects will be assessed at the end of each session on a 0 (not at all) to 10 (highest degree) scale used by Ahn et al. (2019) (37), which includes the following symptoms: 1. Itching; 2. Burning; 3. Headache; 4. Fatigue; 5. Nervousness; 6. Dizziness; 7. Difficulty concentrating. The total score is the sum of the 7 items, varying from 0 to 70. Higher scores indicate higher levels of side effects.

8. Treatment emergent event review: after each RS-tDCS session and clinical assessment, subjects will be asked "Have you had any new symptoms, new medical conditions or been started on new medication/treatment since we last saw you?". This information will help research staff to judge about potential adverse events related to the trial. In addition, changes in treatment will help researchers to account for them in data analysis and the study's results interpretation.

4.1. **STUDY INTERVENTION**

The study intervention is tDCS treatments delivered by the Soterix Medical mini-CT device (https://soterixmedical.com/research/remote/mini-CT). The device is a nonsignificant risk (NSR) device study because it does not meet the definition of a significant risk device under §812.3 (m) of the investigational device exemptions (IDE) regulation (21 CFR §812)

(https://www.accessdata.fda.gov/scripts/cdrh/cfdocs/cfcfr/CFRSearch.cfm?fr=812.3).

The Soterix Medical mini-CT device for the RS-tDCS includes: (1) 1 x 1 mini-CT tDCS device; (2) SNAPstrap headgear, a "cap"-like placement for simple positioning and uniform electrode placement; (3) SNAPpads (individually-packaged pre-moistened sponge), and snap connectors (Figure 1) (39).

[figure not shown]

Figure 1. Remotely supervised (RS-tDCS) Equipment. (1) 1 x 1 mini-CT tDCS device; (2) SNAPstrap headgear: "cap"-like placement for simple positioning and uniform electrode placement; (2a) markers for guidance in placement; (2b) electrode polarity labeling with fixed wiring. (3) SNAPpad: (3a) individually-packaged pre-moistened sponge; perforated packaging for easy opening; (3b) snap connectors. (adapted from Pilloni, G., A. et al., Brain Stimul 15(3): 707-716, http://creativecommons.org/licenses/by-nc-nd/4.0/, DOI: 10.1016/j.brs.2022.04.014). The figure at the bottom simulates an RS-tDCS session.

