Research staff with training in using home-based tDCS by the Soterix Medical will meet with the subject via HIPAA-compliant videoconference previously scheduled. Subjects will be encouraged to find a distraction-free setting to complete treatment sessions. After guiding the subject with the proper adjustment of the SNAPstrap headgear and turning on the 1 x 1 Mini-CT device, research staff will provide the device unlock codes for one-time use to the subject. All ten device unlock codes for one-time use (one for each tDCS session) are obtained previously, just after the device is programmed to active or sham. The device unlock codes for one-time use allow the device to function only once a day, just after the inclusion of the code, with the level of electric current and duration of the session determined by the protocol, both (electric current level and duration of the session) pre-programmed on the device before it is delivered to the subject. Thus, the subject cannot alter the electric current level, the duration of the session, or use the device more than once a day. After each RS-tDCS session, research staff will apply the side effects questionnaire, review the subject's current treatment ("treatment review"), ask about any new or updated mental or physical symptoms since the last assessment (adverse events review), and apply the C-SSRS - screening version (C-SSRS SV) as part of the risk assessment (please, see more details on item "9. RISK TO SUBJECTS"). After the last RS-tDCS session (the tenth session), research staff will apply the feasibility questionnaire and blinding assessment. (Table 1). To assess blinding, the subjects will be asked the following question, "What treatment do you believe you have received??"(47). There will be three possible answers: 1) "active-tDCS"; 2)

"sham-tDCS" or 3) "Don't know". If the answer is "Don't know", research staff will ask "Would you be willing to provide your best guess about the treatment you received?", and could choose from two possible replies: 1) active-tDCS; 2) sham-tDCS (47, 48). We will use the Bang Blinding Index, which varies from -1 to +1, being 1 complete lack of blinding, +1 the opposite guessing, and 0 being related to perfect blinding (48). After the tenth session, the subject will be asked to send back the equipment in the pre-paid mail package to send it back.

Clinical assessments:

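### Read literally, the plan t-tests the side-effect score at each of up to ten sessions with no adjustment and only among attenders; one per-subject summary would be better

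*Combined protocol and SAP*

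**What the plan says.** Section 4, secondary outcome 7, states: "The level of side effects will be assessed at the end of each session". The scale has seven symptoms rated 0 to 10: "The total score is the sum of the 7 items, varying from 0 to 70". Section 8 gives the same timing: "After each RS-tDCS session, research staff will apply the side effects questionnaire". A session that does not take place therefore yields no score.

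The Section 4 table is captioned "Table 1. Study's time points and measures". It marks the side-effects questionnaire in the session column only, not at the day 14, 30 or 60 assessments. Its footnote defines that column: "S1 to S10: remotely supervised transcranial direct current stimulation (RS-tDCS) sessions one to ten".

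Section 17 has one comparative rule, "For each time point established, we will compare groups with a t-test or chi-square test", with the t-test for continuous data and "a p value<0.05 will be considered significant". For this score it gives no summary over sessions, repeated-measures model, analysis set, missing-data rule or multiplicity adjustment.

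On numbers, Section 4 plans up to 80 assessed, "of which 20 will be enrolled and randomized", allocated 1:1, so 10 per arm.

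**The concern.** The sessions are the only time points at which this score exists, so the Section 17 rule applied to it means up to ten t-tests. Two consequences follow.

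- **Multiplicity.** Ten unadjusted looks at one outcome give a substantial chance of an isolated significant session when the arms do not differ. In a 20-subject feasibility trial meant to inform a larger one, such a result could be reported as a tolerability signal.
- **Changing membership.** Each later test uses only subjects still attending. If high scores lead people to stop, the later comparison is made among those who tolerated stimulation best, and the difference moves toward zero. This depends on why subjects stop, which the documents do not predict.

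**Working it through.** **Inputs from the documents.** Ten sessions; 10 per arm (20 subjects, 1:1); threshold 0.05, taken as two-sided because sidedness is not stated; cited dropout of 22% to 25% (Section 17).

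**Inputs not in the documents, hence assumed.** Means, SDs, between-session correlation and stopping pattern of the score. There is no planned figure for this outcome to reproduce: the sample size of 20 is tied to feasibility, without an effect size or SD.

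**1. Chance of at least one p<0.05 with no true difference**

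- Ten independent tests: 1 - 0.95^10 = 0.401.
- Sessions within a subject are correlated, so 0.40 is close to an upper figure. Simulation with 10 per arm and full attendance:

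| Between-session correlation | At least one p<0.05 |
|---|---|
| 0 | 0.41 |
| 0.3 | 0.37 |
| 0.5 | 0.30 |
| 0.7 | 0.22 |
| 0.9 | 0.13 |

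- With dropout: between-subject SD 5 and within-subject SD 4 imply a correlation of 25/(25+16) = 0.61. Stopping at 2.7% per session gives 1 - 0.973^9 = 0.22 lost by session 10. At least one of the ten tests then has p<0.05 in about 28% of trials. A single test on the per-subject mean stays near its nominal 5% (4.6% to about 6% across simulation runs).

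**2. Shift in later sessions if stopping depends on the score**

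Same SDs, scores floored at zero, each subject's underlying mean held constant. The stopping probability after a session is 0.5%, plus 12% if the score exceeds 15 (stronger setting), or 1% plus 8% (weaker setting).

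| Assumed means (sham, active) | Stopping | Difference at S1 | Difference at S10 |
|---|---|---|---|
| 8, 14 | stronger | 5.7 | 4.8 |
| 8, 14 | weaker | 5.7 | 5.1 |
| 8, 9 | stronger | 0.85 | 0.72 |

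- The means of 8 and 14 differ by 6; the floor at zero brings the S1 difference to about 5.7.
- In the first row, session 10 attendance is 84% sham and 62% active. The shift is 5.7 - 4.8 = 0.9 points on a 0-70 scale. The session 10 difference has a sampling SD of about 3.2, so the shift is about 0.9/3.2 = 0.3 of a standard error.
- A much harsher rule, under which every subject leaves after the first score above 1.5 to 2 SD, turns a true difference of 0.8 SD into 0.42 to 0.52 SD at session 10 (correlation 0.5 to 0.7). It also leaves only about 3.4 to 6.7 of 10 active subjects, so it is an extreme illustration.

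**3. Behaviour of the per-subject mean over attended sessions**

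- With constant underlying means it gives 5.7 to 5.8 in the 8-versus-14 settings, close to the S1 difference.
- If side effects fade by half over the course (an assumption), it gives about 4.9, against about 4.2 with full attendance. Early leavers contribute only their higher early scores.

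**The case against.** **Section 17 never names side effects or sessions.** True. The secondary outcomes rated by clinical scale carry explicit day 14, 30 and 60 time frames and outcome 7 does not, so both the ten tests and the restriction to attenders are inferred. The inference is nevertheless the literal one: the table of time points lists the sessions, the score exists nowhere else, and no other rule is given.

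**A reader might infer that the tolerability comparison is distorted in the reassuring direction.** The documents do not support that as a statement of fact. Sections 2, 4.1 and 9 cite 6,779 home sessions with similar sensations in both arms and nobody stopping for poor tolerability. Section 8 screens out subjects who cannot tolerate the current in the orientation test. The cited 22% to 25% dropout is not attributed to side effects. The Section 9 pain rule ends stimulation in that session and does not say that the subject leaves. The bias is a possibility of assumption-dependent size, not an expected result.

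**Stopping is captured elsewhere.** Partly. Early leavers count against the primary completion outcome, and Section 16 compares adverse events by Fisher's exact test in all subjects. This limits the safety consequence, but neither analysis uses the 0-70 score.

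**Extra false positives are the cautious error for tolerability, and no go decision rests on a session-level p-value.** Both are fair and lower the severity. They do not make an isolated p<0.05 interpretable.

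**Conclusion.** The point holds as one about multiplicity, with attrition secondary. Under the literal reading, the chance of at least one spurious significant session is about 28% in the setting with dropout and 13% to 41% over the correlations examined. It exceeds 5% throughout that range and does not depend on why subjects stop.

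The attrition effect arises only if stopping depends on side effects. It is about 1 point in the stronger score-dependent setting and near zero if the arms are similar. All SDs, means and stopping rates behind these figures are assumptions.

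Severity is minor to moderate: this is a secondary outcome in a 20-subject feasibility trial, and no decision rule rests on it.

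**What to change.** In Section 17, exempt the side-effect score from the general rule and state:

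- One prespecified comparison between arms of each subject's mean total score over the sessions attended, including every subject with at least one session, reported with a 95% CI.
- By arm, descriptively and without tests: mean score at each session, worst scores, number of sessions contributed, and reasons for stopping.

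If session-level tests were kept instead, a Bonferroni threshold would be 0.05/10 = 0.005 each. That deals with multiplicity but not with the changing membership.

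**Cost.** Wording in Section 17, plus tabulating reasons for stopping by arm. There are two downsides. Session-specific p-values are lost. The attended-session mean also overweights early sessions for early leavers, so it drifts if side effects change over the course (about 4.9 against 4.2 in the fading example). The number of sessions contributed must therefore be shown beside it.
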